5.3 Laboratory Tests

A urine hCG test will be performed during the Screening Visit and at Day 0 prior to surgery (unless Screening and Day 0 occur on the same day), to determine pregnancy status in all female Subjects of child-bearing potential. If the Subject's urine pregnancy test is positive, the Subject cannot continue in the study and will be considered a screen failure.

Positive and clinically significant wound cultures (superficial or deep) obtained at any time during the study will be documented.

5.4 Concomitant Medications

Concomitant medications will be documented in accordance with the following:

- All medications the Subject is taking at baseline (Screening);
- All medications the Subject is given to treat an AE during the study;
- All antimicrobial medications the Subject is given from time of informed consent and throughout the duration of the study;
- Opioid medications (i.e. morphine) given to the Subject for at least 14 consecutive days after randomization.

For all concomitant medications recorded, only the INITIAL dose is required. Changes in dosage, for the same indication, do not need to be recorded (i.e. the medication does not need to be recorded again with a different dose). If the medication is stopped, record the stop date.

5.4.1 Antimicrobial Use

Antimicrobial use for the treatment of an SSI or other infection not associated with the surgical incision will be prescribed at the discretion of the Investigator. For the surgical procedure, Subjects will receive intravenous antibiotics within 24 hours of the surgical procedure, followed by a course of oral antibiotics.

5.5 Surgical Procedure

Subjects will undergo a functional panniculectomy and/or incisional hernia repair with a vertical, transverse, or fleur-de-lis incision as deemed clinically appropriate by the Investigator. The vertical incision must be at least 20 cm in length and require at least 10 cm of undermining on each side of the incision. The resultant surgical incision (whether vertical, transverse or fleur-de-lis) will be closed with absorbable sutures only, Staples may not be used. Incisional glue may not be used for those subjects randomized to the Customizable treatment arm but may be used for those subjects randomized to the SOC treatment arm. After closure of the incision, length will be measured in centimeters. If a fleur-de-lis incision, the vertical and transverse aspects will be measured separately. All surgical incision measurements must be documented.

5.6 Placement of Customizable and N.P.W.T.

5.6.1 Customizable with ActiV.A.C. Therapy Unit

Subjects randomized to the Customizable arm will receive therapy for 5 (+ 2) days.

Prior to dressing application, a topical skin adhesive (ie Mastisol, benzoin, Cavilon™) will be applied to the area around the closed incision, unless the Subject has a known allergy. The skin adhesive must not come in contact with the closed incision and will be applied after the Customizable foam is in place.

Customizable will be altered to cover the entirety of the incision and the tubing will be attached in close proximity to the center of the dressing. JP drains must not be covered by the dressing. An ActiV.A.C. Therapy Unit will then be connected to Customizable in the operating room and activated immediately.

After powering on the ActiV.A.C. Therapy Unit to deliver 125 mm/Hg of continuous negative pressure to the closed incision, the Investigator will ensure that Customizable is maintaining a seal.

The time of Customizable placement and the ActiV.A.C. Therapy Unit settings must be documented.

Customizable is intended to remain in place for the duration of therapy (at least 5 days) without requiring replacement. However, if Customizable develops a leak and all attempts to mitigate are unsuccessful, the dressing may be replaced to ensure continuity of negative pressure therapy. There is a two dressing replacement limit after the first Customizable is applied. If two replacements are attempted and negative pressure cannot be maintained, therapy will be discontinued and the subject will be treated as clinically appropriate. Customizable replacement will be documented.

5.6.2 Standard of Care Dressing

Subjects randomized to the SOC surgical incision dressing arm will receive SOC dressing for 2 (± 1) days immediately following surgery. The closed incision will be covered with materials which may include: a cyanoacrylate adhesive (applied to the incision), skin adhesive (ie Mastisol, benzoin, Cavilon™) to the area around the incision unless the Subject has a known allergy, dry sterile dressing/gauze, medical tape, and/or steri-strips. At a minimum, a dry sterile dressing must be applied. Advanced wound care dressings and NPWT are disallowed from use in this treatment arm. Any materials used for the SOC dressing will be documented.

5.7 Post-Operative Assessments

5.7.1 Surgical Site Complications (SSC) Assessment

SSC is a collective term used to describe adverse surgical incision events that may occur in the short term following primary closure of a surgical incision. Each event after placement of study treatment through Visit 9 is considered an SSC and will be assessed and documented by the Investigator as indicated in this section.

5.7.1.1 **Dehiscence**: Disruption of a surgical incision. Each instance of dehiscence will be documented as a separate SSC if multiple dehiscences occur along the same incision line. Dehiscence not related to seroma, hematoma or infection will be classified as a primary dehiscence. Dehiscence related to seroma, hematoma or infection will be classified as a secondary dehiscence and the primary cause will be documented. The linear dimensions of the dehiscence must be recorded and categorized as follows:

5.7.1.1.1 **Superficial**: Separation of the skin and subcutaneous tissue but not the muscular fascia

5.7.1.1.2 **Deep**: Separation of the muscular fascia

5.7.1.2 **Surgical Site Infection (SSI) (derived from the CDC definition, Superficial and Deep Only)**:

5.7.2.1.1 **Superficial SSI**: Involves only skin and subcutaneous tissue of the incision and has at least one of the following:

1) Purulent drainage from the superficial incision

-OR-

2) Fluid accumulation with purulent fluid that is drained

-OR-

3) A positive culture with one of the following: i) clinical signs/symptoms (may include pain, tenderness, heat, and/or swelling) or ii) is deliberately opened by a surgeon

-OR-

- 4) Organisms isolated from an aseptically obtained culture of fluid or tissue from the superficial incision

-OR-

- 5) Diagnosis of Superficial SSI by the Investigator or designee

Reporting Instructions for Superficial SSI:

- Do not report a stitch abscess (minimal inflammation and discharge confined to the points of suture penetrations) as an infection.
- Do not report a localized stab wound infection as a SSI, instead report as skin or soft tissue infection, depending on its depth.
- “Cellulitis”, by itself, does not meet the criteria for Superficial SSI.
- If the surgical incision infection involves or extends into the fascial and muscle layers, report as a deep incisional SSI.

5.7.2.1.2 Deep SSI: Involves deep soft tissue (e.g., fascial and muscle layers) of the surgical incision and has at least one of the following:

- 1) Purulent drainage from the deep surgical incision but not from the organ/space component of the surgical site.

-OR-

- 2) An abscess or other evidence of infection involving the deep surgical incision is found on direct examination, during reoperation, or by histopathologic or radiologic examination

-OR-

- 3) A positive culture with one of the following: i) clinical signs/symptoms (may include pain, tenderness, heat, and/or swelling), ii) spontaneously dehisces, or iii) is deliberately opened by the Investigator or designee

-OR-

- 4) Diagnosis of deep SSI by the Investigator or designee

Reporting Instructions for Deep SSI:

- Classify infection that involves both superficial and deep surgical incisions as deep incisional SSI.

- Report culture specimen from superficial incisions as ID (incisional drainage)

5.7.2 Clinically Relevant Interventions (CRI)

If a SSC requires intervention, the procedure must be documented. Any subsequent CRI for a SSC that resolves and then recurs will be documented as a separate CRI.

5.7.2.1 Antimicrobial treatment of SSI: administration of antibiotics, antifungals, or other antimicrobials for the treatment of an infection related to the surgical incision.

5.7.2.2 Percutaneous or Open Drainage (by surgeon): decompression of the fluid accumulation using either:

1) Percutaneous drainage of incisional fluid;

- OR -

2) Open technique (at bedside) drainage of incisional fluid;

- OR -

3) Open surgical intervention (in a procedure room or operating room) drainage of incisional fluid.

If infection is suspected, Customizable should be discontinued, cultures should be obtained, and clinically significant results documented as an adverse event.

5.7.2.3 Debridement: Removal of necrotic, damaged, or infected wound tissue either at the bedside or in the operating room. Debridement involving muscular fascia or deeper tissues should be documented as reoperations.

5.7.2.4 Reoperation: Procedure requiring dissection deeper than the skin and subcutaneous tissue, repair of the muscular fascia, entry into the retro-peritoneum, renal transplant revision or graft removal, flaps, and skin graft procedures.

5.7.2.5 NPWT: Application of NPWT for management of the opened surgical incision (wound).

[figure not shown]
5.7.2.6 Digital Photographs of the Closed Surgical Incision

Digital photographs of the closed surgical incision will be taken at Visits 2, 4, 5, 6, 7, 8 and 9; and at any time there is a SSC. Digital photograph instructions specific to this study will be provided by KCI with the study documents.

5.7.2.7 Incisional Pain Assessment - Visual Analog Scale (VAS)

The VAS is a psychometric, numeric response scale which is used to measure a patient's subjective characteristics or attitudes which cannot be directly measured. The Subject will rate perceived pain of the surgical incision using the VAS. See Figure 4.

Figure 4. Visual Analog Scale

5.8 Adverse Events Reporting

Subjects will be monitored regularly during visits for development of AEs, and data on all AEs will be documented as described in Section 9 of this protocol. KCI, the IRB, and regulatory authorities will be informed in a timely manner about all serious adverse events (SAEs), according to applicable regulatory guidelines. Assessment and reporting of AEs is detailed in Section 9 of this protocol.

6 Study Visits

6.1 Study Visit Calendar

	Visit 1	Visit 2	Visit 3 ⁴	Visit 4 ⁵	Visit 5	Visit 6	Visit 7	Visit 8		
	Screening	Day of Surgery	Post-Op	Post-Op	Post-Op	Post-Op	Post-Op	Follow-Up	Unplanned Visit	Early Withdrawal Visit
	Day - 45 to 0	Day 0	Day 2 (±1)	Day 5 (+2)	Day 10 (± 1)	Day 14 (± 2)	Day 21 (± 3)	Day 30 (± 4)		
Informed Consent	X ¹									
Pre-Operative Inclusion & Exclusion Criteria	X ¹									
Subject Demographics	X ¹									
Physical Exam	X ¹	X ²								
BMI	X ¹									

Medical & Surgical History	X ¹									
Urine Pregnancy Test	X ¹	X ²								
Concomitant Medications	X ¹	X	X	X	X	X	X	X	X	X
Functional Panniculectomy Surgery		X								
Intra-operative Inclusion & Exclusion Criteria ³		X								
Randomization		X								
Incision Site Description		X								
Panniculus Grade/Weight ⁶		X								
Surgical Incision Measurement (length)		X								
Customizable or SOC Application		X								
Digital Photographs of Closed Surgical Incision		X	X	X	X	X	X	X	X ⁷	X ⁷
VAS Pain Assessment			X	X	X	X	X	X	X	X
SSC Assessment			X	X	X	X	X	X	X	X
CRI Reporting			X	X	X	X	X	X	X	X
SOC End of Therapy and Dressing Removal			X						X ⁷	X ⁷
Customizable End of Therapy, Dressing Removal, and Collection of ActiV.A.C. unit				X					X ⁷	X ⁷
Adverse Event Reporting		X	X	X	X	X	X	X	X	X

¹Screening procedures may be performed on Day 0.

²Perform only if Visit 1/Screening occurs prior to Day 0.

³If intra-operative inclusion/exclusion criteria are not met, Subject is a screen failure.

⁴Visit occurs for SOC arm only.

⁵Visit occurs for Customizable arm only.

⁶Perform for panniculectomy Subjects only.

⁷Perform if indicated based upon timing of Visit. See Sections 6.10 and 6.11.

6.2 Visit 1: Screening / Day - 45 up to and including Day 0

The following procedures will be performed and documented:

- ICF
- Subject demographics
- Medical and surgical history
- Pre-operative inclusion and exclusion criteria
- Physical exam (including dermatological exam and surgical site inspection)
- Height, weight, BMI
- Concomitant medications
- Urine for hCG screening (all female Subjects of child-bearing potential)

6.3 Visit 2: Day of Surgery / Day 0

The following procedures will be performed and documented:

- Repeat physical exam (including dermatological exam and surgical site inspection), if Visit 1 occurs prior to Day 0
- Repeat urine for hCG screening (all female Subjects of child-bearing potential), if Visit 1 occurs prior to Day 0
- Baseline pre-operative VAS pain assessment of surgical incision site
- Surgical procedure
- Panniculus grade/weight
- Intra-operative inclusion/exclusion criteria
- Randomization
- Incision type, location and measurement (length in cm) (measure the vertical and transverse aspects of fleur-de-lis separately)
- Digital photographs of the closed surgical incision (AP & LAT)
- Customizable or SOC dressing placement by random assignment
- Concomitant medications
- AE reporting

6.4 Visit 4: Post Operative / End of SOC Therapy / Day 2 (±1) – SOC Arm Only

The following procedures will be performed and documented:

- SOC surgical incision dressing removal
- VAS pain assessment of surgical incision
- Digital photographs of the closed surgical incision (AP & LAT)
- SSC assessment
- CRI reporting
- Concomitant medications
- AE reporting

6.5 Visit 5: Post Operative /End of Customizable Therapy / Day 5 (+2) – Customizable Arm Only

The following procedures will be performed at least 2 hours after dressing removal, and documented:

- Customizable removal and collection of ActiV.A.C. unit
- VAS pain assessment of surgical incision
- Digital photographs of the closed surgical incision (AP & LAT)
- SSC assessment
- CRI reporting
- Concomitant medications
- AE reporting

6.6 Visit 6: Post Operative Assessment / Day 10 (± 1)

The following procedures will be performed and documented:

- VAS pain assessment of surgical incision
- Digital photographs of the closed surgical incision (AP & LAT)
- SSC assessment
- CRI reporting
- Concomitant medications
- AE reporting

6.7 Visit 7: Post Operative Assessment / Day 14 (± 2)

The following procedures will be performed and documented:

- VAS pain assessment of surgical incision
- Digital photographs of the closed surgical incision (AP & LAT)
- SSC assessment
- CRI reporting
- Concomitant medications
- AE reporting

6.8 Visit 8 Post Operative Assessment / Day 21 (± 3)

The following procedures will be performed and documented:

- VAS pain assessment of surgical incision
- Digital photographs of the closed surgical incision (AP & LAT)
- SSC assessment
- CRI reporting
- Concomitant medications
- AE reporting

6.9 Visit 9: Post Operative Assessment / Day 30 (± 4)

The following procedures will be performed and documented:

- VAS pain assessment of surgical incision
- Digital photographs of the closed surgical incision (AP & LAT)
- SSC assessment
- CRI reporting
- Concomitant medications
- AE reporting

6.10 Early Withdrawal Visit

The following procedures will be performed and documented, as applicable:

- Customizable or SOC surgical incision dressing removal
- Collection of ActiV.A.C. unit
- VAS pain assessment of surgical incision
- Digital photographs of the closed surgical incision (AP & LAT)
- SSC assessment
- CRI reporting
- Concomitant medications
- AE reporting

6.11 Unplanned Visit

The following procedures will be performed and documented, as applicable:

- Customizable or SOC surgical incision dressing removal
- Collection of ActiV.A.C. unit
- VAS pain assessment of surgical incision
- Digital photographs of the closed surgical incision (AP & LAT)
- SSC assessment
- CRI reporting
- Concomitant medications
- AE reporting

7 Study Discontinuation and Withdrawal of Study Subjects

7.1 Premature Discontinuation of the Study

If the study is terminated prematurely or suspended, the IRB will be informed promptly and provided with the reason(s) for the termination or suspension by KCI or by the Investigator. If applicable, regulatory authorities and the personal physicians of the Subjects will also be informed.

7.1.1 By Sponsor

KCI reserves the right to discontinue any study for business or ethical reasons at any time, such as, but not limited to:

- The study is not conducted in accordance with the approved protocol
- Information on the study product causes doubt as to the benefit/risk ratio
- Changes in medical practice limit utility of the data obtained from the study.

KCI reserves the right to terminate a study at an investigative site at any time based on the terms and conditions set forth in the Clinical Research Agreement (Section "Termination"), or for other good cause, including, but not limited to, any of the following reasons:

- Investigator(s) lack of compliance to protocol and/or with applicable regulatory or IRB guidelines in conducting the study
- Incidence or severity of AEs indicates a potential health hazard or poses an unreasonable risk to the study participants
- Subject enrollment is unsatisfactory.

7.1.2 By IRB

The IRB may choose to discontinue the study at the site for which they granted approval if the:

- Study is not conducted in accordance with the IRB 's requirements
- Study is associated with unexpected serious harm to Subjects.

7.2 Premature Discontinuation of Subject

Subjects will be discontinued from the study if their randomly assigned treatment is ended prematurely, or if Customizable cannot maintain a seal even after replacing the dressing twice (see Section 5.6.1).

Subjects may withdraw from participation in the study at any time at their own request, or they may be withdrawn at any time at the discretion of the Investigator for safety, behavioral, or administrative reasons. If a Subject does not return for a scheduled visit, every effort should be made to contact the Subject, per the site's local protocol.

In any circumstance, every effort should be made to document Subject outcome. The Investigator should inquire about the reason for withdrawal, request that the Subject return for a final visit, if applicable, and follow-up with the Subject regarding any unresolved AEs. Any related SAEs occurring within 14 days following Subject discontinuation must be reported to KCI, and any applicable regulatory agencies and must be followed until stabilization or resolution.

If the Subject withdraws from the study, and also withdraws consent for disclosure of future information, no further study evaluations will be performed, and no additional data will be collected. The Investigator may retain and continue to use any data collected before such withdrawal of informed consent.

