10.2 Subject Populations for Analysis

There are two principle analysis populations for this clinical study:

10.2.1 Full Analysis Set (FAS) Population – The FAS subject population will consist of all Subjects who i) met all of the pre-operative and intra-operative inclusion criteria and none of the pre-operative and intra-operative exclusion criteria, ii) have been randomized, and iii) received treatment with either Customizable or SOC dressing. Subjects without SSC will need to receive at least 5 days of Customizable or at least 1 day of SOC dressing to be included in this set and completed Visit 9/Day 30 (\pm 4 days). Subjects with SSC prior to Visit 9/ Day 30 (\pm 4 days) will be included in this set regardless of length of Customizable or SOC dressing treatment and treatment follow up. Subject data will be analyzed in the arm to which they were randomized and treated. The primary and secondary effectiveness analyses for this study will be based on the FAS population.

10.2.2 Safety Population (SP) / Intent-to-Treat (ITT) – The safety population / ITT will consist of all Subjects who are randomized and do not withdraw before the attempt to apply the assigned treatment with Customizable or SOC surgical incision dressing regardless of its duration. Subject data will be analyzed in the arm to which they were randomized. All safety results and supportive analyses for this study will be presented based on the safety population.

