5.2 Sample Size and Power

Per the protocol, at the time of the trial design,

“A 35% rate of SSC is projected for the SOC arm, which is consistent with the clinical experience of the Investigators. Based on the primary endpoint of incidence rate of SSC, Fisher’s exact test with a two-sided significance level $\alpha = 0.05$ will have approximately 80% power to detect the difference between an incidence rate of 35% in the SOC arm and an incidence rate of 8.75% in the Customizable arm (a 75% reduction) when the sample size in each arm is 44. To account for possible Subject replacement, the sample will be increased by up to 15% for a maximum total of 102 Subjects (51 in each treatment arm).”

The study was terminated early before it reached the final planned sample size of 102 subjects. The study enrollment was stopped on Friday, June 30, 2017. The decision of early termination was made after the interim data review described in Section 10 of this document. A total of 71 subjects (36 in Customizable™, 35 in SOC) were enrolled in this study.

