5.3 Analysis Populations

The following subject populations for this clinical study are:

Safety Population – The Safety population will consist of all subjects who are randomized and do not withdraw before the attempt to apply the assigned treatment with Customizable™ or SOC surgical incision dressing regardless of its duration. Subject data will be analyzed in the arm to which they were treated. All safety results for this study will be presented based on the safety population.

Intent-to-Treat (ITT) Population – The ITT population will consist of all subjects who are randomized and do not withdraw before the attempt to apply the assigned treatment with Customizable™ or SOC surgical incision dressing regardless of its duration. Subject data will be analyzed in the arm to which they were randomized. All supportive or exploratory analyses for this study will be presented based on the ITT population.

Full Analysis Population (FAS): The FAS subject population will consist of all subjects who i) met all of the pre-operative and intra-operative inclusion criteria and none of the pre-operative and intra-operative exclusion criteria, ii) have been randomized, and iii) received treatment with either Customizable™ or SOC dressing. Subjects without SSC will need to receive at least 5 days of Customizable™ or at least 1 day of SOC dressing to be included in this set and completed Day 30 (\pm 4 days). Subjects with SSC prior to Day 30 (\pm 4 days) will be included in this set regardless of length of Customizable™ or SOC dressing treatment and treatment follow up. Subject data will be analyzed in the arm to which they were randomized and treated. The primary and secondary effectiveness analyses for this study will be based on the FAS population.

Subjects having important disqualifying protocol deviations will be excluded from ITT and/or FAS based on the results from the protocol deviation review described in Section 5.4 of this document.

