5.4 Conventions, Definitions and Handling of Missing Data/Dropouts

5.4.1 General Considerations

- Summaries of continuous variables will show the number of non-missing values (n), along with mean, median, standard deviation, minimum and maximum. In general, the maximum and minimum values will be presented to the same precision as the raw data; the mean and median will be presented to one decimal place more than the raw data. The standard deviation and confidence intervals (CI) will be presented to two decimal places more than the raw data. Exceptions for number of decimal places may be made according to the data. The p-values will be presented to four decimal places. A p-value less than 0.0001 will be presented as < 0.0001 or $< .0001$.
- Listings of all available data recorded on the case report form (CRFs) will be presented. There will be no imputation of missing data, with the exception of partially missing dates.
 - Each analysis variable with partial dates will be reviewed at the time of analysis and final decision will be made at that point on the appropriate imputation strategy. All

subject listings data will be provided as recorded on the CRFs indicating the partial dates and missing data. If needed, footnote(s) for imputed dates will be added to the data listings.

- If data are missing or incomplete and the variable is used in a calculation then the derived variable will be set to missing. Similarly in the summary tables of analyses the variable will be considered missing.
- The most recent assessment prior to the Day 0 surgery or prior to the opening of the randomization envelope will be used as the baseline reference for all analyses which incorporate a baseline value.
- All end-of-study analyses will use the last recorded observation (last visit) during the study.
- All subjects enrolled in the study who received either Customizable™ or SOC will be included in the summary of safety profile.

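### Ending the assigned dressing early also ends study follow-up, so early stoppers with no recorded SSC leave the primary FAS, mainly by design on Customizable, and their ITT outcome needs one clear rule

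*Protocol*

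**What the plan says.** **Leaving the study.** Protocol 7.2 makes early end of treatment a reason for leaving the study: "Subjects will be discontinued from the study if their randomly assigned treatment is ended prematurely". It adds seal failure after two replacements as a second trigger. For that same seal failure, Protocol 5.6.1 says only that "therapy will be discontinued and the subject will be treated as clinically appropriate". Protocol 5.7.2.2 gives another reason for stopping the device: "If infection is suspected, Customizable should be discontinued, cultures should be obtained".

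**What follow-up remains.** Protocol 7.2 asks for every effort to document outcome and for a final visit where applicable. The Early Withdrawal Visit (6.10) includes an SSC assessment. Sections 7.2 and 9.7 add limited adverse-event follow-up.

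**Primary set.** Protocol 10.2.1 admits event-free subjects on conditions: "Subjects without SSC will need to receive at least 5 days of Customizable or at least 1 day of SOC dressing", together with a completed Day 30 visit. SAP 5.3 repeats this, and says that subjects with an SSC before Day 30 "will be included in this set regardless of length of Customizable™ or SOC dressing treatment and treatment follow up".

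**Supportive ITT.** SAP 5.3 keeps early stoppers in the ITT, and SAP 7.1 repeats the rate formula and Fisher test there. Two general conventions in SAP 5.4.1 bear on an outcome not followed to Day 30: "If data are missing or incomplete and the variable is used in a calculation then the derived variable will be set to missing" and "All end-of-study analyses will use the last recorded observation (last visit) during the study".

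**The concern.** Follow-up for the primary endpoint stops for a reason tied to treatment, and inclusion in the primary set then depends on whether an event had already been recorded. The 7.2 rule is worded for both arms, but the exposure is unequal. Customizable runs 5 to 7 days against 1 to 3 for SOC, the FAS minimum is 5 days against 1, and the seal and suspected-infection triggers name Customizable only. SSI is a component of the endpoint, so suspicion of an endpoint event can itself lead to exit.

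At stake is how an arm difference should be read when some Customizable outcomes were not looked for up to Day 30. After the interim review, that difference is an unfavourable one.

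**Working it through.** **1. What the rules do to an early stopper who leaves under 7.2**

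| Status at exit | FAS | ITT by the SAP 7.1 formula or the last-visit sentence | ITT by the set-to-missing sentence |
|---|---|---|---|
| SSC recorded | in, event | in, event | in, event |
| No SSC recorded | out (no Day 30; on Customizable usually under 5 days too) | in, non-event | out |

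**2. The plan's own figures.** SAP 10 gives 29 Customizable and 32 SOC subjects in the interim FAS, with rates of 17.2% and 3.1%. These are 5/29 = 17.2% and 1/32 = 3.1%. Treated but outside the FAS: 70 − (29 + 32) = 9. The design power also reproduces: exact enumeration for 35% against 8.75% with 44 per arm gives 80.7%, against the stated 80% or so. This point does not alter it.

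**3. Arm split of the nine.** SAP 5.2 states: "A total of 71 subjects (36 in Customizable™, 35 in SOC) were enrolled in this study". Assume the 70 treated are among those 71. The treated arms are then 36/34, leaving 36 − 29 = 7 Customizable and 34 − 32 = 2 SOC outside the FAS, or 35/35, leaving 6 and 3.

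**4. Two-sided Fisher tests, assuming none of the nine had a recorded SSC**

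| Handling of the nine | 36/34 | 35/35 |
|---|---|---|
| Excluded (FAS, or set to missing): 5/29 vs 1/32 | p = 0.093 | p = 0.093 |
| All event-free: 5 vs 1 | 13.9% vs 2.9%, p = 0.20 | 14.3% vs 2.9%, p = 0.20 |
| Unseen Customizable all SSC, SOC none | 12/36 vs 1/34, p = 0.0014 | 11/35 vs 1/35, p = 0.0029 |
| Unseen SOC all SSC, Customizable none | 5/36 vs 3/34, p = 0.71 | 5/35 vs 4/35, p = 1.0 |

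Counting all nine as SSCs in both arms gives 12/36 vs 3/34, p = 0.019, or 11/35 vs 4/35, p = 0.078. Both lie inside the range above, so such a row is not a bound.

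**5. Direction in the FAS.** With k unseen Customizable SSCs, the rate over all treated is (5 + k)/36 or (5 + k)/35. For k = 0, 1, 2, 3 this is 13.9, 16.7, 19.4, 22.2% of 36, or 14.3, 17.1, 20.0, 22.9% of 35. The FAS rate of 17.2% is too high for k = 0, about right for k = 1 and too low from k = 2.

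**6. False superiority, for the event-free ITT reading only.** Model: 36 vs 35, equal true rate π in both arms, observed Customizable rate π(1 − s), leavers kept in the denominator, rejection when Fisher p ≤ 0.048 with Customizable lower. The unseen share s is an assumption.

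| True SSC rate π | s = 0 | s = 10% | s = 20% |
|---|---|---|---|
| 6/61 = 9.8% (pooled interim) | 1.5% | 2.0% | 2.7% |
| 17.2% | 2.1% | 3.2% | 4.9% |

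**The case against.** Four points on the other side have weight.

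- **Exit is not blind.** The withdrawal visit includes an SSC assessment, suspected infection is to be cultured, and the investigator's diagnosis alone qualifies as SSI under Protocol 5.7.1.2. A reader might infer that infections leading to exit are lost from the endpoint. The documents do not support that: an infection confirmed at exit counts and keeps the subject in the FAS. The exposed events are infections not confirmed at exit, and later dehiscence or SSI.
- **The ITT text is not evenly split.** A reader might see a head-on contradiction in SAP 5.4.1. The SAP 7.1 formula and the last-visit sentence agree on a non-event, and Protocol 10.9 uses all recorded data without an imputation algorithm. Only a general convention on derived variables points the other way. This stands, and it reduces the need to one clarifying sentence.
- **The nine may have nothing to do with 7.2.** The review was triggered when about 60 subjects had completed, so some may simply have been still in follow-up, or ineligible. Early stoppers with an SSC are in the FAS and so not among the nine. Nine therefore caps only interim-date exits with no recorded SSC.
- **Enrolment has stopped.** A protocol change helps little here. SAP 6.1 already reports discontinuation reasons, and SAP 7.1 already repeats the test on the ITT.

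What remains is that no text preserves the scheduled SSC visits after exit, and that FAS membership depends on the recorded outcome.

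**Conclusion.** The point holds as a design weakness of uncertain and possibly negligible size. Protocol 7.2 and 5.6.1 differ on whether seal failure ends study participation or only therapy. Following 7.2, event-free early stoppers leave the primary set while those with an event stay, and by design this falls mainly on Customizable.

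A reader might infer that the FAS flatters Customizable or could produce a false claim of benefit. The documents do not support either. The direction depends on the number of unseen events (step 5). The rise in false-superiority risk (step 6) belongs to the event-free ITT reading, not to the primary FAS, and rests on an assumed unseen share. At the interim rates Customizable is higher even under the most favourable assignment (14.3% against 11.4%), so no superiority conclusion could arise.

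The range of p from 0.0014 to 1.0 is illustrative. It assumes that the 70 treated are among the 71 enrolled and that none of the nine had a recorded SSC, and it treats all nine outcomes as unknown, though some may have become known since. The importance lies between minor and should-fix.

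**What to change.** 1. **Protocol.** Reconcile 5.6.1, 5.7.2.2 and 7.2 on study status only: early end of the dressing is treatment discontinuation, and scheduled SSC, CRI and AE assessments continue through Visit 9 unless consent is withdrawn. No rule on when to stop a dressing changes. Section 7.2 already bars further evaluations only when consent for future information is also withdrawn, so the existing text allows this. It helps only subjects not yet exited, or a later study.
2. **SAP 5.4.1 and 7.1.** State one ITT rule for an SSC not observed to the end of follow-up.
3. **Sensitivity rows.** Use any SSC documented after exit up to Day 34. On the ITT, show all early stoppers event-free, then two opposite-assignment bounds: unobserved Customizable counted as SSC with unobserved SOC as none, and the reverse.
4. **SAP 6.1.** Add day of exit and SSC status at exit, by arm, to the planned discontinuation summary.
5. **Primary set.** Keep the FAS as primary, because interim rates by arm have been seen. Show the analysis without the minimum-duration clause as a sensitivity only. Dropping that clause restores only early stoppers who completed Day 30, so it does not replace the bounds.

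Cost: one SAP sentence, two table columns and a few sensitivity rows, with no change to the primary analysis; under item 1, continued visits for a few early stoppers.
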